5.3.1.5. Dose Modification for Hepatic Impaired Subjects

Ibrutinib is metabolized in the liver. For subjects who develop mild liver impairment while on study (Child-Pugh class A), the recommended dose reduction for ibrutinib/placebo is to a level of 280 mg daily (two capsules). For subjects who develop moderate liver impairment (Child-Pugh class B), the recommended dose reduction is to a level of 140 mg daily (one capsule). Subjects who develop severe hepatic impairment (Child-Pugh class C) must hold study drug until resolved to moderate impairment (Child-Pugh class B) or better, and could be re-treated according to resolved hepatic conditions (ie, 140 mg or 280 mg for moderate or mild impairment, respectively). Monitor subjects for signs of toxicity and follow dose modification guidance as needed (refer to [Appendix K](#)).

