1.8.1. Pharmacokinetics and Product Metabolism

Following oral administration of ibrutinib at doses ranging from 1.25 to 12.5 mg/kg/day as well as fixed dose levels of 420, 560, and 840 mg/day, exposure to ibrutinib increased as doses increased with substantial intersubject variability. The mean half life ($t_{1/2}$) of ibrutinib across 3 clinical studies ranged from 4 to 9 hours, with a median time to maximum plasma concentration (T_{max}) of 2 hours. Administration of 420 mg ibrutinib with a high-fat breakfast in subjects with CLL approximately doubled the mean systemic exposure compared to intake after overnight fasting with median time to T_{max} delayed from 2 to 4 hours. Ibrutinib was extensively metabolized to the dihydrodiol metabolite PCI-45227, a reversible inhibitor of Btk, with approximately 15 times lower inhibitory potency compared to ibrutinib. The metabolite-to-parent AUC ratio ranged from 0.7 to 3.4. Steady-state exposure of ibrutinib and PCI-45227 was less than 2-fold of first dose exposure.

The results of human mass balance study of [¹⁴C]-ibrutinib conducted in six healthy male subjects demonstrated that less than 10% of the total dose of [¹⁴C]-ibrutinib is renally excreted, whereas approximately 80% is recovered in feces. Subjects with mild and moderate renal insufficiency (creatinine clearance >30 mL/min) were eligible to enroll in Study PCYC-1102-CA in which pharmacokinetic (PK) assessments were included. No dose adjustment is needed for mild or moderate renal impairment (greater than 30 mL/min creatinine clearance). There is no data in patients with severe renal impairment or patients on dialysis. In a hepatic impairment study, data showed an increase in ibrutinib exposure. Following single dose administration, the AUC of ibrutinib increased 2.7-, 8.2- and 9.8-fold in subjects with mild (Child-Pugh class A), moderate (Child-Pugh class B), and severe (Child-Pugh class C) hepatic impairment compared to subjects with normal liver function. The safety of ibrutinib has not been evaluated in patients with hepatic impairment.

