1.9.3. Justification of Study Design and Dose Rationale

While rituximab has shown efficacy in a prophylactic role against cGVHD, rituximab used with corticosteroids has provided only partial efficacy in steroid-refractory or new onset cGVHD. Furthermore, rituximab alone does not deplete alloreactive B cells once cGVHD has developed. Ibrutinib has the potential to improve upon the efficacy of rituximab due to its unique mechanism of action on B cells in combination with its potential to reverse ITK polarization, thus causing a skewing away from a Th2 cytokine profile.

Btk occupancy $>95\%$ has been demonstrated in all patients who received Ibrutinib dosed 2.5 mg/kg/day or higher. Modest toxicity has been reported at 420 and 840 mg daily. Common AEs reported were gastrointestinal upset (diarrhea, nausea, vomiting), fatigue, respiratory infections, and rash. Because these AEs may overlap with cGVHD manifestations, a conservative dose of 420 mg will be used as the starting dose for this trial. This dose is currently approved for use in relapsed/refractory CLL with an acceptable safety profile. At 420 mg daily, Dubovsky et al. (2013) reported 40-80% ITK occupancy (Dubovsky 2013). If the 420 mg dose demonstrates unacceptable toxicity in the cGVHD population then the dose will be lowered to 280 mg/day which is also expected to produce full BTK occupancy. If further dose reduction is required due to toxicity, a dose of 140 mg daily will be used and is the lowest dose recommended in the FDA package insert for ibrutinib.

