 11. Moderate or severe hepatic impairment (Child-Pugh classification, see [Appendix K](#)).
 12. Subject has a concurrent illness which in the opinion of the investigator may interfere with the treatment and evaluation of the patient.
 13. Concomitant use of warfarin or other Vitamin K antagonists
 14. Subject has a known allergy or hypersensitivity to ibrutinib.
 15. Vaccinated with live, attenuated vaccines within 4 weeks of first dose of ibrutinib.
 16. Known bleeding disorders (eg, von Willebrand's disease or hemophilia).
 17. History of stroke or intracranial hemorrhage within 6 months prior to enrollment.
 18. Known history of human immunodeficiency virus (HIV) or active with hepatitis C virus (HCV) or hepatitis B virus (HBV). Subjects who are positive for hepatitis B core antibody, hepatitis B surface antigen, or hepatitis C antibody must have a negative polymerase chain reaction (PCR) result before enrollment. Those who are PCR positive will be excluded.
 19. Major surgery within 4 weeks of first dose of ibrutinib.
 20. Concurrent use of a strong cytochrome P450 (CYP) 3A inhibitor ([Appendix I](#)).
 21. Unable to swallow capsules or malabsorption syndrome, disease significantly affecting gastrointestinal function, or resection of the stomach or small bowel, symptomatic inflammatory bowel disease or ulcerative colitis, or partial or complete bowel obstruction.
 22. Unable to understand the purpose and risks of the study and to provide a signed and dated informed consent form (ICF) and authorization to use protected health information (in accordance with national and local subject privacy regulations).

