5.2. Study Treatment

5.2.1. Phase 1b Dose Selection and Stopping Rules

Three dose levels of ibrutinib may be tested: 140 mg/day, 280 mg/day and 420 mg/day. The starting dose will be 420 mg/day and the dose will be modified based on the dose limiting toxicities (DLTs).

Phase 1b will follow a modified 3+3+3 design with 6-9 subjects at each dose level. The dose will be selected as the RP2D if the subject incidence of DLTs during the first 28 days of study treatment is <33%. Before determining the RP2D, 6 subjects in any given cohort must have completed the DLT observation period which is defined as 28 days of therapy. Using the modified 3+3+3 design, the maximum tolerated dose (MTD) is exceeded when ≥ 3 out of 9 subjects in a dose level experience a DLT. If there are 3 DLTs at a dose level, the MTD is exceeded and then the next lower dose level will be enrolled.

Enrollment in a dose level will proceed as follows:

- If no DLT is observed during the DLT observation period in the initial 3 subjects of a dose level, then a second group of 3 subjects will be enrolled at the same dose level for a total of 6 subjects. If 0-1 DLT occur out of 6 subjects, then this dose will be the RP2D. If 2 DLTs occur out of 6, then the dose level cohort will be expanded to enroll a total of 9 subjects. If no further DLTs occur then this dose will be the RP2D.
- If 1 DLT is observed in the initial 3 subjects, the dose level will be expanded to enroll 3 additional subjects at the same dose level for a total of at least 6 subjects. If no further DLT(s) are observed, then this dose will be the RP2D. If 2 DLTs are observed out of 6 subjects, then the dose level will be expanded to enroll a total of 9 subjects. If no further DLTs are observed in this group of subjects then this dose will be the RP2D.
- If 2 DLTs are observed in the initial 3 subjects, then enrollment to this dose level will be stopped. A DLT review will occur to determine if the dose should be lowered.
- If 3 DLTs are observed, then the dose level will be stopped and the next lower dose will be assessed.

If a subject experiences a DLT during the DLT observation window, the subject will discontinue treatment.

The decision to proceed with a RP2D or to dose reduce will be made in a Dose Level Review Meeting by the Sponsor in conjunction with the investigators after careful consideration of all available safety and laboratory information.

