5.2.2. Definition of Dose Limiting Toxicities

The following DLT criteria apply only to Phase 1b of the study. After completing the DLT period (28 days), Phase 1b subjects will be evaluated by standard safety reporting.

A DLT is defined as any drug-related hematologic or non-hematologic toxicity Grade 3 or higher, with the following exceptions:

- Grade 4 nausea, vomiting, or diarrhea or Grade 3 diarrhea defined by ≥ 7 stools/day persisting for greater than 3 days despite best supportive care
- Grade 4 neutropenia or Grade 3 neutropenia persisting for greater than 14 days or Grade 3 neutropenia of any duration with fever
- For subjects with Grade 2 rash at entry, DLT will be progression to Grade 3 AND a doubling of % BSA involvement
- For subjects with Grade 3 rash at entry, DLT will be progression to Grade 4 OR a doubling of % BSA involvement

5.2.3. Phase 2

Following the establishment of the RP2D, the Phase 2 portion of the study will begin accruing additional subjects. Approximately 40 subjects (cumulative from both Phase 1b and Phase 2) will be treated with the RP2D. Subjects enrolled in the Phase 2 part of the study will have met the same inclusion/exclusion criteria as Phase 1b subjects and will be treated with the RP2D. Subjects continuing from Phase 1b and subjects enrolled in Phase 2 will continue to be treated unless they have intervening unacceptable toxicity or meet other criteria for subject discontinuation (see [Section 9](#)).

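### The 280 mg dose for mild hepatic impairment applies only when it develops on study; subjects who enter with it start at 420 mg, and Child-Pugh class A alone does not identify them.

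*Protocol*

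**What the plan says.** **On-study rule.** Protocol Section 5.3.1.5: "For subjects who develop mild liver impairment while on study (Child-Pugh class A), the recommended dose reduction" (for study drug) "is to a level of 280 mg daily (two capsules"). Class B leads to 140 mg. Class C means holding the drug until recovery to class B or better, then 140 or 280 mg according to the class reached. The section refers to Appendix K.

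**Entry.** Exclusion 11 in Section 4.2 reads "Moderate or severe hepatic impairment (Child-Pugh classification", with a reference to Appendix K. Mild impairment is not excluded.

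**Starting dose.** Section 5.2.1: "The starting dose will be 420 mg/day and the dose will be modified based on the dose limiting toxicities (DLTs"). Section 5.2.3: Phase 2 subjects "will have met the same inclusion/exclusion criteria as Phase 1b subjects and will be treated with the RP2D". Neither section, nor 5.3.1.2 on administration, gives a different starting dose for mild impairment.

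**Evidence cited.** Section 1.8.1 reports that, after a single dose, "the AUC of ibrutinib increased 2.7-, 8.2- and 9.8-fold in subjects with mild (Child-Pugh class A"), moderate and severe impairment respectively, compared with normal liver function. It adds: "The safety of ibrutinib has not been evaluated in patients with hepatic impairment". Section 1.9.3: "Modest toxicity has been reported at 420 and 840 mg daily".

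**Appendix K.** Five items score 1 to 3 points each. Class A is 5-6 points, B is 7-9 and C is 10-15.

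**The concern.** The protocol treats mild impairment as enough reason to cut the dose by a third, but only when it appears after the first dose. The same liver state on Day 1 draws the full dose, and no text explains the difference. Elsewhere the protocol handles raised exposure without regard to when its cause began: under Section 6.2.1, a moderate CYP3A inhibitor that must be used means 140 mg for as long as it is used.

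The second difficulty is the label. The rule names class A as the grade that goes with 280 mg, but a subject with five normal items is also class A. Two investigators facing the same laboratory values could reasonably give different doses.

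What is at stake is the safety of a subgroup whose exposure the protocol itself describes as raised, and consistent dosing across sites. The primary response analysis and its sample size are not in question.

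**Working it through.** **1. Class boundaries (Appendix K).** The minimum total is 5 × 1 = 5 and the maximum is 5 × 3 = 15. This reproduces the lower end of the plan's class A range, 5-6. Of the 3^5 = 243 score patterns, none falls below class A and six are class A: one with every item normal (5 points) and five with a single item at 2 points (6 points). The other 90 are class B and 147 are class C. These are counts of patterns, not of patients. With B and C excluded, every eligible subject scores 5 or 6 at entry. A change from 5 to 6 does not change class. A subject who recovers from class C to five normal items is again class A, the class that 5.3.1.5 pairs with 280 mg.

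**2. Can a subject enter with 6 points?** Set Appendix K beside the Section 4.1 limits:
- Albumin of 2.8-3.5 g/dL scores 2 points. There is no entry limit on albumin.
- Mild ascites scores 2 points. There is no entry limit on ascites.
- Bilirubin of 2-3 mg/dL scores 2 points. The entry limit is 2 × ULN. If ULN is 1.0 to 1.3 mg/dL (assumption), the limit is 2.0 to 2.6 mg/dL, so part of that range is admitted.
- INR of 1.71-2.30 scores 2 points. The entry limit is below 1.5 × ULN, so 1.71 passes only if ULN exceeds 1.71 / 1.5 = 1.14, or under the exception stated in the criterion.

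Entry with 6 points is therefore possible. The documents do not say how often it occurs. Purely for scale, an assumed share of 5% to 20% would be 40 × 0.05 = 2 to 40 × 0.20 = 8 subjects. Those percentages have no source.

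**3. Dose gap.** 420 / 280 = 1.5, and 1 − 280/420 = 33%.

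**4. Exposure.** Take 420 mg with a normal liver as 1, apply the 2.7-fold ratio, and let AUC vary as dose to the power b. Section 1.8.1 says only that exposure rose with dose, with substantial variability, so b = 0.8 to 1.2 is an assumption.
- Class A at 420 mg: 2.7.
- Class A at 280 mg: 2.7 × (280/420)^b = 1.95, 1.80 and 1.66 for b = 0.8, 1.0 and 1.2.
- Normal-liver dose matching 420 mg in class A: 420 × 2.7^(1/b) = 1454, 1134 and 961 mg for the same b.

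All three equivalents lie above the 840 mg of Section 1.9.3. The range straddles the 1400 mg/day reached without an MTD (Section 5.3.1.3). Applying 2.7 to a 6-point entrant is a further assumption, because the mix of 5- and 6-point subjects behind that ratio is not given.

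**The case against.** The best defence is that 5.3.1.5 should be read clinically. Its condition is new liver impairment, and the class in brackets only grades it. Section 1.8.1 likewise sets mild impairment apart from normal liver function. On this reading a healthy subject with 5 points has no impairment and the rule works. That part stands. A reader might infer from Appendix K that the 280 mg step can never be triggered, or that it applies to everyone on Day 1; the wording does not require either. What remains is that no criterion separates a normal from a mildly impaired liver at 5-6 points, and the clinical reading leaves the gap at entry untouched.

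Three other inferences are tempting and unsupported:
- *That entry limits of 3 × ULN for AST, ALT and alkaline phosphatase make 6 points common.* None of these is a Child-Pugh item.
- *That a DLT in such a subject would wrongly count against 420 mg.* Under the present criteria it should count, since Phase 2 enrols the same population. The review meeting also weighs all the safety data.
- *That 420 mg is shown to be unsafe in mild impairment.* It is not. Modest toxicity is reported at 840 mg and no MTD was reached up to 1400 mg/day. A high-fat breakfast also roughly doubles exposure (Section 1.8.1), and 5.3.1.2 imposes no fasting.

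There are also safeguards. The investigator may exclude for concurrent illness (exclusion 12), and the Medical Monitor approves each eligibility checklist. Chemistry is drawn on Day 1 and at Weeks 2 and 5, then every four weeks to Week 25. PK is sampled in Weeks 1 and 2, and Table 1 governs toxicity. These reduce the risk, but none sets a starting dose for mild impairment.

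**Conclusion.** The point holds in a limited form. Subjects with mild impairment at entry are eligible and start at 420 mg, or at the RP2D if that is 420 mg. Subjects who reach the same state later are recommended 280 mg. The plan gives no reason for this 1.5-fold difference, although it reports raised exposure and no safety evaluation in hepatic impairment. Class A alone cannot identify who should step down.

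The dose gap and the class arithmetic come straight from the documents. The exposure equivalents depend on the assumed dose-exposure relation and on carrying a single-dose ratio over to 6-point entrants. The number of subjects affected is unknown, harm is possible but not shown, and the reduction is a recommendation. If the RP2D is 280 or 140 mg, the discrepancy closes in Phase 2. A reader might conclude that all 6-point candidates must be excluded; that is a preference, and the documents do not make it necessary. The correction is worth making because it is small and applies the protocol's own dose rule consistently.

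**What to change.** 1. **Screening.** Record the Child-Pugh score. Bilirubin, albumin, PT/INR and the physical examination are already collected then.
2. **Section 5.3.1.5.** Reword it to cover subjects who have or develop hepatic impairment: 6 points attributed to liver dysfunction, 280 mg or the assigned dose if lower; 7-9 points, 140 mg; 10-15 points, hold. Requiring attribution to the liver avoids reductions for Gilbert's syndrome or non-hepatic low albumin. Newly recognised impairment still at 5 points would remain a matter of judgement and Table 1; say so.
3. **Phase 1b.** Do not enter subjects with 6 points from liver dysfunction into the 420 mg DLT cohort, because they would no longer be started at that dose.
4. **Section 10.1.** The efficacy population currently requires at least one dose at the RP2D. Define it so that Phase 2 subjects started at 280 mg under this rule are kept, and confirm that the SAP's All Treated Population, used for efficacy in SAP Section 5, does the same.
5. **Optional.** Ask for a current local PT/INR whenever the score is recalculated, since it is scheduled only at Screening.

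If 420 mg at entry is intended, state the reason and reconcile the on-study rule with it.

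The cost is a few sentences and no new Screening test. A few subjects may receive 280 mg instead of the RP2D, and no Phase 2 candidate is lost.

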5.3.2. Management of Immunosuppression

Participants may be receiving other immunosuppressive therapies (including extra-corporeal photopheresis [ECP]) in addition to glucocorticoids. In addition, due to potential drug-drug interactions with ibrutinib, drug levels for immunosuppressant agents such as cyclosporine, tacrolimus, and/or sirolimus are highly recommended during the clinical trial. The doses for these immune-suppressants should be adjusted per institutional practices based on the measured drug level. Changes in immunosuppressive medications being used for the treatment of cGVHD should not be altered during the DLT window unless levels are documented to be at sub-therapeutic or toxic levels. Concurrent use of sirolimus and a calcineurin inhibitor (tacrolimus or cyclosporine) are prohibited.

5.3.3. Management of Steroids

Systemic steroids may be decreased at the treating physician's discretion. The initial taper of steroids may begin two weeks following initiation of ibrutinib if a clinical response is seen. The recommendation is to not taper below 50 percent of the original dose by the 12-week assessment period unless there is a documented medical reason for steroid reduction below 50 percent (eg, uncontrolled diabetes, infection). A specific steroid taper schedule will not be mandated.

Because cGVHD by its nature is a protean disease with clinical manifestations that wax and wane over time, closely spaced clinical evaluations will detect temporary exacerbations of cGVHD manifestations but may not accurately reflect the long term trajectory of a subject's cGVHD and response to treatment. Therefore, in the event a participant experiences a flare of cGVHD, a temporary increase in steroids will be allowed until symptoms return to baseline or criteria are met for progressive cGVHD. If criteria are met for progressive cGVHD, the participant will be scored as a treatment failure and removed from the study.

Non-absorbable oral steroids will be allowed and recorded.

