The Screening Phase assessments will be performed within 42 days prior to study treatment. Eligible subjects will have clinically determined cGVHD and are dependent on or been refractory to steroids. Subjects may have had no more than 3 previous therapies for cGVHD and must have GVHD involvement in at least one of the following categories:

- >25% body surface area (BSA) NIH-defined criteria “Erythematous rash”
- >4 total mouth score by NIH-defined criteria

Study subjects must have a stable or worsening cGVHD assessment for a minimum of 14 days before starting ibrutinib.

[figure not shown]
The Treatment Phase will extend from first dose of study treatment until DLT in Phase 1b or until disease progression, unacceptable toxicity, recurrence of underlying malignancy, or study

closure in Phase 2. During the Treatment Phase, efficacy and safety evaluations will be performed according to the Schedule of Assessments in [Appendix A](#).

The Post-treatment Follow-up Phase will begin once a subject discontinues ibrutinib treatment:

- Subjects who discontinue for reasons other than disease progression (ie, for adverse event or Investigator decision), will complete an End-of-Treatment Visit (30 ± 3 days from the last dose of ibrutinib) and will be followed until death, lost to follow-up, consent withdrawal, or study end, whichever occurs first:
 - Continued disease evaluations
 - Follow-up for recurrence of malignancy
 - Follow-up for new cGVHD treatments
- Subjects who discontinue due to disease progression will complete an End-of-Treatment Visit and be followed for survival status.

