8.3.2. Long-Term Follow-up

Once subjects progress (for subjects who have not withdrawn consent), they will be contacted approximately every 3 months (± 14 days) by clinic visit or telephone to assess survival. Subjects will be contacted until death, subject withdrawal, lost to follow-up, or study termination by the Sponsor, whichever occurs first.

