9.2. Withdrawal from Study Treatment

Study treatment will be discontinued in the event of any of the following events:

- cGVHD progression (see definition in [Section 7.2.1](#))
- Unacceptable toxicity: an intercurrent illness or AE that prevents further ibrutinib administration.
- Noncompliance with study medication.
- Investigator's decision (such as chronic noncompliance, significant protocol deviation, or best interest of the subject)
- Withdrawal of consent for treatment by subject
- Malignancy progression/relapse.
- Subject's condition no longer requires study treatment.
- Subject becomes pregnant
- Study termination by Sponsor
- Death

All subjects, regardless of reason for discontinuation of study treatment will undergo an End-of-Treatment Visit and be followed for progression and survival.

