9.3. Withdrawal from Study

Withdrawal from study (including all follow-up) will occur under the following circumstances:

- Withdrawal of consent for follow-up observation by the subject
- Lost to follow-up
- Study termination by Sponsor
- Death

If a subject is lost to follow-up, every reasonable effort should be made by the study site personnel to contact the subject. The measures taken to follow up should be documented.

When a subject withdraws before completing the study, the following information should be documented in the source documents:

- Reason for withdrawal;
- Whether the subject withdraws consent (ie, withdraws consent to treatment and all further contact) or withdraws consent to treatment but agrees to participate in follow-up visits.

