10.2. Endpoints

10.2.1. Primary Endpoints

Phase 1b:

Safety and Tolerability

Drug toxicity will be described and graded according to [CTCAE v. 4.03](#) criteria. Dose limiting toxicities are defined in [Section 5.2.2](#). Only toxicities which occur during the first 28 days on ibrutinib will count towards the assessment of DLTs.

Toxicities which occur after the first 28 days for Phase 1b subjects will be described and graded according to [CTCAE v. 4.03](#) criteria and presented in tabulated form. This will also be performed for subjects enrolled in the Phase 2 portion of the study.

Phase 2:

The primary efficacy endpoint is the best overall cGVHD response rate. Best overall cGVHD response rate is defined the proportion of subjects who achieve a NIH-defined complete response or partial response.

Please refer to [Section 7.2.1](#) for the definition of overall cGVHD response.

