5.1 Primary Endpoint

The primary efficacy endpoint is the best overall cGVHD response rate during the study based on investigator assessments. To assess the primary endpoint, the study used the 2005 NIH Consensus Panel Response criteria with two modifications based on the updated 2014 NIH Consensus Panel Response criteria: 1) “Not Evaluable” can be used for assessments where there is another non-cGVHD cause for the abnormalities documented and 2) a change in cGVHD organ score from 0 to 1 is no longer considered progression as is the case per the 2005 NIH cGVHD Response Criteria.

Best overall cGVHD response rate is defined as the proportion of subjects who achieve a NIH-defined complete response or partial response. The response rate and its 95% confidence interval (CI) will be calculated based on the exact test for binomial distribution. If the lower bound of the CI of the response rate is $\geq 25\%$, the primary efficacy objective is achieved.

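### Protocol Section 5.3.3 removes a subject from the study at cGVHD progression, contradicting the sections that keep progressed subjects in follow-up

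*Protocol*

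**What the plan says.** Protocol Section 5.3.3 allows a temporary steroid increase for a cGVHD flare. It then states that if progression criteria are met, "the participant will be scored as a treatment failure and removed from the study". The sentence closes the paragraph on flares, but its condition is general and is not limited to subjects on a raised steroid dose.

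Other sections describe what follows progression:

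- Section 9.2 lists cGVHD progression first under "Study treatment will be discontinued in the event of any of the following events". It ends: "All subjects, regardless of reason for discontinuation of study treatment will undergo an End-of-Treatment Visit and be followed for progression and survival".
- Section 3.1: "Subjects who discontinue due to disease progression will complete an End-of-Treatment Visit and be followed for survival status".
- Section 8.3.2: "Once subjects progress (for subjects who have not withdrawn consent), they will be contacted approximately every 3 months", in order to assess survival.
- Section 9.3 opens with "Withdrawal from study (including all follow-up) will occur under the following circumstances". It names withdrawal of consent for follow-up, loss to follow-up, termination by the sponsor, and death. Progression is not on the list.

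On response, protocol Section 10.2.1 reads "Best overall cGVHD response rate is defined the proportion of subjects who achieve a NIH-defined complete response or partial response", and SAP Section 5.1 gives the same definition.

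**The concern.** The protocol separates two things: stopping study treatment (Section 9.2) and leaving the study with all its follow-up (Section 9.3). Section 5.3.3 uses the language of the second for an event that the protocol lists under the first. An investigator managing a flare would read 5.3.3 and could reasonably end all contact at progression.

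At stake are data that the protocol otherwise expects from subjects whose disease has worsened: the End-of-Treatment Visit, the last part of adverse event collection, survival status and new malignancies. Two of the three FFS failure types, death and a new cGVHD treatment, depend directly on contact after progression. Losing them would remove information selectively from the subjects most likely to fail.

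**Working it through.** This is mainly a comparison of text. The documents give no figure on this point to reproduce.

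**1. What ends at progression.**

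| Section | At cGVHD progression |
|---|---|
| 5.3.3 | Subject leaves the study |
| 9.2 | Treatment stops; End-of-Treatment Visit; progression and survival follow-up |
| 3.1 | End-of-Treatment Visit; survival follow-up |
| 8.3.2 | Contact about every 3 months for survival |
| 9.3 | Not a ground for study withdrawal |
| Appendix A | Columns for an End-of-Treatment Visit and for survival follow-up |

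Read literally, 5.3.3 stands alone against the rest.

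**2. What a literal reading of 5.3.3 could lose.**

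- The End-of-Treatment Visit (Section 8.2.2), due about 30 days after the last dose or before a new cGVHD treatment. It includes a review of adverse events and of any new cGVHD treatment. The Progressive Disease Visit (Section 8.2.1) would probably still take place, but a treatment started because of progression would usually begin after it.
- The rest of the adverse event window, which runs to 30 days after the last dose (Sections 7.1.6 and 11.4.2).
- Deaths found through Long-Term Follow-up (Section 8.3.2).
- New malignancies, which Section 11.4.6 wants reported during follow-up after progression as well.
- Relapse of the underlying malignancy. The clearest loss is within the 30-day window. Beyond that, Section 3.1 itself asks only for survival status in progressed subjects.

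Long-term collection of later cGVHD treatments in progressed subjects should not be charged to 5.3.3. Section 7.1.5 already limits it to subjects who stop without progression.

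**3. Effect on FFS.** SAP Section 5.3 and its Table 2 count death, a new cGVHD treatment and recurrence of malignancy as failures. Progression of cGVHD is not one. A subject removed at progression with no earlier failure would therefore be censored at the last date known to be failure-free. Such subjects probably fail sooner than those still under observation, so FFS would tend to be overstated.

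The possible size per subject can be bounded. Take the planned 40 subjects, *k* failures by time *t*, and no other censoring.

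- Complete data: FFS = (40 − *k*)/40.
- One failure unrecorded, with that subject censored after *j* of the other failures: FFS = [(40 − *j*)/40] × [(40 − *k*)/(39 − *j*)].
- Rise = (40 − *k*)/[40 × (39 − *j*)].
- Since *j* ≤ *k* − 1, we have 39 − *j* ≥ 40 − *k*, so the rise is at most 1/40 = 2.5 percentage points.

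**4. Effect on the primary endpoint.** None.

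- Protocol 10.2.1 and SAP 5.1 count subjects who achieve CR or PR. Neither has a clause that cancels a response on later progression.
- Duration of response (protocol 10.2.2.2, SAP 5.2.2) is defined in responders only, with progression as an event. If progression cancelled responder status, that event could never occur.
- The treatment-failure label is not defined anywhere and is not an input to any endpoint or to the sample size calculation in Section 10.3.

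**The case against.** **Loose drafting.** Section 8.3.1 speaks of subjects discontinuing the study who are nonetheless seen in clinic every 12 weeks, so it plainly means discontinuing treatment. The removal wording in 5.3.3 can be read the same way, and the operative visit and withdrawal sections agree with each other. This stands as a reason for low severity. It does not remove the conflict, because Section 9.3 gives study withdrawal a specific meaning that covers all follow-up.

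**Limited consequence.** FFS is exploratory. If a new cGVHD treatment is recorded at or soon after progression, that is already an FFS failure and a later death adds nothing. Duration of response ends at progression, so no planned primary or secondary efficacy analysis needs survival data afterwards. All of this stands. What remains is that recording the new treatment depends largely on the contact that 5.3.3 would cut off, and that the safety and malignancy data matter in their own right.

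**A stronger reading that does not hold.** A reader might infer that scoring progressed subjects as treatment failures turns earlier responders into non-responders, so that the primary rate depends on which section is followed. The documents do not support this. No endpoint uses the label, the response definition rests on achieving CR or PR, and duration of response requires that responders who progress remain responders. Any calculation of a reduced response rate would also need a count of responders who later progress, which the documents do not give.

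**Conclusion.** The point holds as an internal contradiction of low severity. Section 5.3.3 takes a progressed subject out of the study, while Sections 3.1, 8.3.2 and 9.2 keep that subject in follow-up and 9.3 gives no ground for removal.

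The primary endpoint and its power do not change. The possible harm is lost safety and survival data after progression and probably informative censoring of an exploratory endpoint, at no more than 2.5 percentage points of FFS per unrecorded failure under the conditions shown. The total effect cannot be estimated, since it depends on how many subjects progress without a recorded failure and how many sites follow 5.3.3 literally. That the censoring would be informative is a judgement, resting on the assumption that subjects with worsening cGVHD are at higher risk of the FFS events.

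**What to change.** Reconcile Section 5.3.3 with Sections 3.1, 8.3.2, 9.2 and 9.3. Replace the removal wording with a cross-reference to Sections 9.2 and 8.3.2, so that a progressed subject has the End-of-Treatment Visit and then enters Long-Term Follow-up. Delete the treatment-failure label, or state that it has no role in best overall response and that a CR or PR documented before progression still counts.

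This concerns follow-up and scoring only and takes no position on when treatment should stop. It costs one sentence in an amendment, adds no visits beyond those already scheduled, and needs no change to the SAP.
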